 - a. Our study will have 3 groups for evaluation: G1 control (Invisalign on a 2week aligner schedule) and 2 intervention groups, G2 and G3 (each on an accelerated 4 days aligner schedule). The only difference between the intervention groups will be the use of vibration (G2 with vibration vs G3 without vibration). The expected rate of tooth movement for G1 will be .04mm/day (.25mm/week or .5mm/2 weeks) while the expected rate of tooth movement for G2 and G3 will be .28mm/day (.5mm in 4 days). The standard deviation is assumed 0.1 for three groups. Based on our sample calculation to achieve an adequate power, we will attempt to recruit a total of 42 patients to account for a dropout rate of 30%. Ideally, we would like to have a total sample size of 21 patients to ensure each of 3 study groups will have 7 patients, which will achieve more than 0.8 power even under a Bonferroni correction for multiple comparisons.
- 4. Randomization:
 - a. Our patients will be randomly allocated into the 3 groups based on a block randomization with size 6. The list will be independently generated by our study biostatistician.
- 5. Type I error and statistical significance:
 - a. P values less than .05 will be considered statistically significant in the overall test
- 6. Inclusion Criteria:
 - a. Males or females over the age of 18 years old desiring orthodontic treatment.

- b. Adult dentition with all upper and lower front teeth present and any premolar and molar combination in the upper posterior of two teeth on each side.
- c. Normal pulp vitality and healthy periodontal tissues as determined by intraoral exam.
- d. Good health as determined by medical history.
- e. Willingness and ability to comply with study procedures, attend study visits, and complete the study.
- f. The ability to understand and sign a written informed consent form, which must be signed prior to initiation of study procedures.
- 7. Exclusion Criteria:
 - a. Patient under the age of 18 years old
 - b. Patients diagnosed with systemic diseases such as diabetes, hypertension (high blood pressure), temporomandibular disorders (jaw disorders), or craniofacial syndromes.
 - c. Severe malocclusions that would require adjunctive procedures other than Invisalign. These include impacted teeth, closure of extractions spaces.
 - d. Significant periodontal disease (> 4mm pocket depth or >2 mm of recession on upper anterior teeth).
 - e. Active caries not under care of either a dentist or periodontist.

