 - f. Chronic daily use of any non-steroidal anti-inflammatory medication, estrogen, calcitonin, or corticosteroids.
 - **g.** History of use or current use of any bisphosphonate medication or other medication for treatment of osteoporosis.
 - h. Current smoker (must not have smoked in the last 6 months).
 - i. Failing to comply with research protocols
- 8. Arms:
 - a. Control Group (G1): 14 patients, standard Invisalign therapy with 2 week aligner schedule
 - a. Intervention Group (G2): 14 patients, accelerated Invisalign + vibration
 i. AcceleDent device 20 minutes/day per manufacturer's instructions

b. Intervention Group (G3): 14 patients, accelerated Invisalign + no vibration

- 7. Clinical Trial Protocol:
 - a. Visit #1: Clinical Screening with UNC Orthodontic Faculty (clinical purposes only)
 - i. Brief discussion of findings with patient and eligibility for Invisalign
 - b. Visit #2: Clinical exam and records (clinical purposes only), 30 days post visit #1
 - i. Completion of medical history
 - ii. Completion of extra and intra oral exams
 - iii. Completion of alginate impressions
 - iv. Photographs (extra and intra oral)
 - v. Xrays- Panoramic and Cephalometric
 - c. Visit #3: Treatment Plan Presentation (Experimental Baseline), 60 days post visit #1

- i. Clinical Procedures:
 - 1. Treatment plan presentation
 - a. Each treatment plan will be approved by [name] who will be blinded to a patient's study participation
 - 2. Invisalign impressions with PVS material
- ii. Research Procedures:
 - 1. Study recruitment
 - 2. Informed Consent
 - 3. iTero intraoral scan
 - 4. Completion of the Inclusion/Exclusion Case Report Form
- d. Visit #4: (120 days post visit #1/Day #1 of active treatment)
 - i. Clinical Procedures:
 - 1. Intraoral exam and intraoral photographs
 - 2. Deliver aligner number 1 and usage instructions
 - ii. Research Procedures:
 - 1. Deliver AcceleDent Aura device along with instructions
 - 2. Collection of gingival crevicular fluid biomarkers
 - 3. Completion of Faces Pain Scale
 - 4. Deliver daily diaries
- e. Visit #5: (125 days post visit #1/ Day #5 of active treatment)
 - i. Clinical procedures:
 - 1. Deliver aligners 2-4 to accelerate Invisalign groups and aligner schedule instructions
 - ii. Research Procedures:
 - 1. iTero intraoral scan
 - 2. Collection of gingival crevicular fluid biomarkers
 - 3. Completion of Faces Pain Scale and Adverse Event Form
- f. Visit #6: (134 days post visit #1/Day #14 of active treatment)

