 - a. Patients who experience an adverse event or reaction such as: uncontrolled pain or allergy will be disenrolled from the study and allowed to continue Invisalign therapy using the standard two-week aligner schedule. In addition, non-compliant patients will be disenrolled from the study and recommend to continue Invisalign therapy using the standard protocol.
- 10. Data Analysis:
 - a. Tooth leveling and alignment
 - i. Little's Index
 - b. Tooth rotations and translations
 - i. Euler's Law of Motion (6 degrees of freedom)
 - ii. 3D surface mapping
 - c. Alternative measurement options
 - i. Screw Method
 - d. Inflammation biomarkers within gingival crevicular fluid
 - i. ELISA
 - e. Orthodontic Pain Assessment
 - i. Faces Pain Scale
- 11. Statistical Analysis:
 - a. In order to complete statistical analysis for maxillary and mandibular dentition, we will compare the five time points within each group as well as the three groups across each time point.
 - b. Our primary statistical method will be a three-way repeated measurement ANOVA, with the main effects being: vibration, aligner schedule, and time. The ANOVA measurement will identify significant differences within the data and the post hoc comparison will determine which specific variables are involved. In order for a relationship to be considered statistically significant, the p-value must be less than .05.
 - c. One additional method for statistical analysis could be a survival analysis which would be more favorable in the case our study experiences a high volume of drop-outs during treatment.
- 12. Patient Confidentiality:
 - a. Records related to this research study that involve perennial information will only be accessible by the primary research committee and direct assistants. Records will be stored on encrypted, password-protected computer hard drives. A 3-digit code number will be used rather than the subject's name to identify the specific data related to his/her involvement in the study. Only the research investigators will have access to the file that links personal

information to the 3-digit codes, and this file will be stored in a separate location from the actual research data.

Project Timeline:

Item	Date
Study Design; IRB submission ([name])	Spring 2016
Background Research	March 2016
Loose conceptual framework	March 2016
Presentation	April 2, 2016
Protocol	May 16, 2016
IRB approval	May 2016
Select study population	August 2016
Clinical Trial	November 2016

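### The accelerated-arm rate in the power analysis contradicts itself (.5 mm in 4 days is .125 mm/day, not .28), and the claim of power above 0.8 depends on which figure is meant

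*Combined protocol and SAP*

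**What the plan says.** The Power Analysis section sets out three inputs:

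- Control arm: "expected rate of tooth movement for G1 will be .04mm/day (.25mm/week or .5mm/2 weeks").
- Both accelerated arms: "expected rate of tooth movement for G2 and G3 will be .28mm/day (.5mm in 4 days").
- Spread: "The standard deviation is assumed 0.1 for three groups", with no unit.

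From these it concludes that 21 patients, 7 per group, are enough, "which will achieve more than 0.8 power even under a Bonferroni correction for multiple comparisons". It does not give the number of comparisons, the sidedness or the test. The Type I error section adds only that "P values less than .05 will be considered statistically significant in the overall test". The Arms section lists 14 patients in each group, for example "14 patients, standard Invisalign therapy with 2 week aligner schedule" for the control arm. Under Statistical Analysis the method is different again: "Our primary statistical method will be a three-way repeated measurement ANOVA", with vibration, aligner schedule and time as the main effects.

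**The concern.** The two figures for the accelerated rate differ by a factor of 0.28/0.125 = 2.24, which rounding cannot explain. The control figures in the same sentence do agree with each other.

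This input sets the effect size. The difference from control is 0.24 mm/day on one figure and 0.085 to 0.089 mm/day on the other. The paragraph is the trial's only sample-size justification. If the smaller rate was intended and the SD is in mm/day, a reader of a non-significant standard-versus-accelerated comparison would be leaning on a power figure that the inputs do not support.

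**Working it through.** **Inputs (Power Analysis section)**

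- Control rate: 0.04 mm/day as printed, or 0.25/7 = 0.0357 unrounded.
- Accelerated rate: 0.28 mm/day as printed, or 0.5/4 = 0.125 mm/day from the parenthesis. Conversely, 0.28 × 4 = 1.12 mm in 4 days.
- SD: 0.1, read here as mm/day, the unit of the two rates compared (assumption).
- n = 7 per group.
- Alpha 0.05. Main case: two-sided with three pairwise comparisons, so 0.05/3 each (assumption).

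**Differences**

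- Printed rate: 0.28 − 0.04 = 0.24, so d = 0.24/0.1 = 2.4.
- Rate from the parenthesis: 0.125 − 0.04 = 0.085 (d = 0.85), or 0.125 − 0.0357 = 0.0893 (d = 0.893) with the unrounded control rate. Ranges below run over these two values.

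**Formulas**

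- Pairwise t test: noncentral t with 2n − 2 df and noncentrality d√(n/2).
- Overall three-group F test, with two arms at the same rate: noncentral F with 2 and 3n − 3 df and noncentrality n × (2/3) × d².
- Control versus both accelerated arms pooled: noncentral t with 3n − 2 df and noncentrality d/√(1/n + 1/(2n)).

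**Step 1. The plan's own figure.** With d = 2.4 and n = 7, the noncentrality is 2.4 × √3.5 = 4.49, against a critical value of 2.78 on 12 df. Power is 0.94. The claim of more than 0.8 reproduces with 0.28.

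**Step 2. The same test with 0.125.** The noncentrality is 0.85 × √3.5 = 1.59, or 1.67 with the unrounded control rate. Power is 0.16 to 0.18.

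**Step 3. Other choices the plan leaves open, with 0.125.**

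| Test | 7 per group | 14 per group |
|---|---|---|
| One pairwise t test, two-sided, 0.05/3 | 0.16–0.18 | 0.39–0.44 |
| Overall F test, 0.05 | 0.31–0.34 | 0.60–0.65 |
| Control vs pooled accelerated, two-sided 0.05 | 0.41–0.45 | 0.72–0.76 |
| Control vs pooled accelerated, one-sided 0.05, unadjusted | 0.55–0.59 | 0.82–0.85 |

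At 7 per group, the pairwise Bonferroni variants tried (two or three comparisons, one- or two-sided, 12 or 18 df) run from 0.16 to 0.35. The pooled contrast one-sided at 0.05/2 gives 0.41 to 0.45. If 30% drop out of 14 per group, 9 to 10 remain, and power is 0.23 to 0.29 (pairwise, 0.05/3) or 0.40 to 0.48 (F test).

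**Step 4. Sensitivity to the SD's unit, with 0.125 and 7 per group.**

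- For 0.8 power at two-sided 0.05/3, the SD must be about 0.043 to 0.045 mm/day or less.
- If 0.1 is mm/week: (0.875 − 0.25)/0.1 = 6.25, power above 0.99.
- If 0.1 is mm per 4 days: (0.5 − 0.143)/0.1 = 3.57, power above 0.99.

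**Step 5. Detectable difference.** With SD 0.1 mm/day and two-sided 0.05/3, 80% power needs a difference of about 0.20 mm/day at 7 per group and 0.13 at 14.

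**Attrition (secondary).** The plan says "we will attempt to recruit a total of 42 patients to account for a dropout rate of 30" per cent. But 1 − 21/42 = 50%, while 30% loss leaves 42 × 0.7 = 29.4 patients. This errs on the safe side.

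**The case against.** The strongest reply is that the power loss is conditional twice: 0.125 must be the intended rate, and the SD must be in mm/day. Neither is established. Both schedules move 0.5 mm per aligner interval, which favours 0.125 but does not prove it. An SD of 0.1 mm/day is also awkward beside a control mean of 0.04: it is 2.5 times the mean, and under normality about 34% of control patients would show negative movement. This stands, so low power cannot be called a fact. The contradiction between the two rates needs neither condition. An unstated unit that moves power from 0.16 to above 0.99 is itself a reason to rewrite the paragraph.

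Two further points are fair:

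- The planned analysis is a repeated-measures ANOVA over five time points, and every figure above is for a single-measurement comparison. Power for the ANOVA cannot be computed, because no within-subject correlation is given. The figures test the plan's claim in the terms in which the plan states it: group rates, one SD and a Bonferroni correction.
- The pairwise figures are for each comparison separately. The chance that at least one of the two control-versus-accelerated tests is significant is higher: by simulation 0.26 to 0.29 at 7 per group and 0.55 to 0.60 at 14. Both remain below 0.8.

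It can also be said that the central hypothesis, on vibration, is untouched. That is true, but only because both accelerated arms carry the same expected rate, so the paragraph offers no power for that hypothesis under either figure.

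**Conclusion.** The concern holds. The printed rate and its parenthesis cannot both be right, and the document does not show which is meant. With SD 0.1 in mm/day, the power claim at 7 per group is sound on 0.28 and fails on 0.125 under every variant tried, the most favourable being a one-sided, unadjusted pooled contrast that the plan does not name. Retaining all 14 per group would make the overall F test more likely than not to detect the difference, but still short of 0.8; only the one-sided pooled contrast would pass. The contradiction is certain. The size of the power loss depends on the rate intended and on the SD's unit. It must be fixed because the sole justification of the sample size depends on this input.

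**What to change.** Reconcile the two accelerated rates, and state the SD's unit, the test, the sidedness and the number of comparisons. Then:

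- **If 0.5 mm in 4 days is the intended input and the SD is in mm/day:** replace .28 with .125, withdraw the claim of power above 0.8, and write, for example:

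> With SD 0.1 mm/day, power for each of G1 versus G2 and G1 versus G3, taken separately, is about 0.16–0.18 with 7 per group and 0.39–0.44 with 14 (two-sided t tests, three Bonferroni comparisons). For the overall F test it is 0.31–0.34 and 0.60–0.65. The difference detectable with 80% power under Bonferroni is about 0.20 mm/day with 7 per group and 0.13 with 14. These figures are for a single-measurement comparison, not for the repeated-measures ANOVA.

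- **If .28 is intended and the SD is in mm/day:** correct the parenthesis and give the source of .28. The power claim can then stand.
- **If the SD is in another unit:** state it and recompute.

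In each case, say that the calculation covers standard versus accelerated schedules and not the vibration comparison. Optionally, restate the attrition allowance: 42 covers 50% loss down to 21.

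The cost is one rewritten paragraph, with no extra patients or procedures. In the first case the stated power becomes much less favourable.

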Methods: Approximately 42 patients, between the ages of 18-65 years, will be consecutively recruited to participate in a randomized prospective clinical trial. Enrolled subjects will be randomly allocated into one of 3 groups: Standard Invisalign therapy (G1-control), Accelerated Invisalign therapy + vibration (G2) and Accelerated Invisalign therapy without vibration (G3). Data collection will include intra oral scans of both the maxillary and mandibular dentition at 5 different time points: TO (baseline), T1 (4 days), T2 (14 days), T3 (6 weeks) and T4 (12 weeks). In addition, PerioPaper strips will be used to sample gingival crevicular fluid at each of the time points listed above. Research subjects will also be asked to complete a daily diary regarding their pain level during treatment. Data analysis will be used to specifically evaluate alignment of adjacent teeth and translational, and/or rotational, tooth movement will be evaluated by superimposing digital models recorded at the specific time points. Inflammation biomarkers will be analyzed with ELISA. Finally, the

statistical significance of our data will be evaluated with a 3 way repeated ANOVA as well as a post hoc comparison with Bonferri correction. P values less than .05 will be considered statistically significant.

Specific Aims:

In this study, we propose a randomized prospective clinical design to investigate effects of vibration therapy, using an AcceleDent Aura® device, on the rate of orthodontic tooth movement, activation of gingival crevicular fluid inflammation biomarkers and patient discomfort in conjunction with accelerated Invisalign therapy.

Hypothesis:

We propose vibration therapy will accelerate orthodontic tooth movement, increase inflammation biomarkers and reduce pain for orthodontic patients.

Background:

Align Technology©, Inc. developed Invisalign® in 1997 to meet the esthetic demands of orthodontic patients and providers. Invisalign patients receive a series of computer-assisted designed stereolithic clear retainers to incrementally resolve their malocclusion. Invisalign® and other advances in orthodontic technology such as clear aligners, ceramic brackets and lingual braces offer options to address the esthetic demands of most orthodontic patients but duration of treatment continues to be one of the most challenging aspects of practice.²

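### The power claim cannot cover vibration, because G2 and G3 are planned at the same rate; for the other comparisons it holds only at the printed .28 mm/day, not at the bracketed .5 mm in 4 days

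*Combined protocol and SAP*

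**What the plan says.** The Specific Aims put vibration first: "we propose a randomized prospective clinical design to investigate effects of vibration therapy". The Hypothesis is that vibration speeds tooth movement, raises inflammation biomarkers and reduces pain. Under Statistical Analysis (Methods section 11), vibration is one of three main effects in the primary repeated-measures ANOVA, with aligner schedule and time.

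The Power Analysis (Methods section 3) gives these inputs:

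- G1 is expected to move at .04 mm/day, explained as .5 mm per 2 weeks.
- On the two accelerated groups: "The only difference between the intervention groups will be the use of vibration (G2 with vibration vs G3 without vibration").
- Their rate is a single figure: "expected rate of tooth movement for G2 and G3 will be .28mm/day (.5mm in 4 days").
- On spread: "The standard deviation is assumed 0.1 for three groups". No unit is printed.
- On numbers, the aim is a "total sample size of 21 patients to ensure each of 3 study groups will have 7 patients", and "we will attempt to recruit a total of 42 patients to account for a dropout rate of 30" per cent. The Arms section lists 14 patients in each group.
- The conclusion drawn for 7 per group is "which will achieve more than 0.8 power even under a Bonferroni correction for multiple comparisons".

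The section does not say which comparison has this power, how many comparisons the correction covers, or whether the tests are two-sided.

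**The concern.** G2 vs G3 is the only contrast that isolates vibration. With equal expected rates the planned difference is zero, so no sample size calculation for it was possible from these inputs. A power statement that mentions multiple comparisons and excludes none will still be read as including it.

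The Background asks whether vibration and its cost are justified. The plan does not say that a non-significant result will be read as no vibration effect. A general claim of more than 0.8 power nevertheless invites that reading, in a trial that never specified the effect it could detect.

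Aligner schedule is also a genuine question of the trial (Abstract, Significance; Methods section 11), and the claim can apply there. That part, however, depends on a rate that its own bracket contradicts.

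**Working it through.** **Assumptions not stated in the plan.** One rate per patient; SD 0.1 in mm/day, the unit of the headline rates; two-sided tests; three pairwise comparisons for Bonferroni (alpha 0.05/3 = 0.0167).

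**Formulas.** For n per group:

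- Pairwise contrast with difference d: noncentral t, δ = d / (SD × √(2/n)), df = 2n − 2.
- Overall one-way test of three groups at alpha 0.05: noncentral F, λ = n × Σ(mean − grand mean)² / SD², df = 2 and 3n − 3.

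**Step 1: reproduce the plan's figure.** Rates .04, .28, .28; n = 7.

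- Overall: grand mean 0.20; sum of squares 0.16² + 0.08² + 0.08² = 0.0384; λ = 7 × 0.0384 / 0.01 = 26.9; power 0.993.
- G1 vs G2 or G3: d = 0.24; δ = 0.24 / (0.1 × √(2/7)) = 4.49; power 0.984 at 0.05 and 0.938 at 0.05/3.

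The claim of more than 0.8 therefore reproduces for these comparisons.

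**Step 2: the vibration contrast at the plan's rates.** d = .28 − .28 = 0. The probability of rejection is alpha itself: 0.05, or 0.0167 after correction. Using the bracketed rate for both groups gives the same result.

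**Step 3: check the rate against its bracket.** .5 / 4 = 0.125 mm/day, whereas .28 × 4 = 1.12 mm. Rounding does not explain this: the G1 bracket agrees with its rate (.5 / 14 = 0.036, printed as .04).

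**Step 4: repeat step 1 at 0.125 mm/day.** d = 0.125 − .04 = 0.085. The plan does not state a figure of 10 per group; it follows from its recruitment and dropout: 42 × 0.7 / 3 = 9.8.

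| n per group | Overall test | G1 contrast, 0.05 | G1 contrast, 0.05/3 |
|---|---|---|---|
| 7 | 0.31 | 0.31 | 0.16 |
| 10 | 0.44 | 0.44 | 0.26 |
| 14 | 0.60 | 0.58 | 0.39 |

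Reaching 0.8 would take 22 per group for the overall test and 31 for the G1 contrast at 0.05/3.

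**Step 5: what G2 vs G3 could show.** Solving step 1's contrast formula for d at power 0.80, with 95% CI half-width = t(0.975, 2n − 2) × 0.1 × √(2/n):

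| n per group | Detectable, 0.05 (mm/day) | Detectable, 0.05/3 (mm/day) | CI half-width (mm/day) |
|---|---|---|---|
| 7 | 0.163 | 0.197 | 0.116 |
| 10 | 0.132 | 0.157 | 0.094 |
| 14 | 0.110 | 0.130 | 0.078 |

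At 7 or 10 per group the detectable difference exceeds the entire bracketed rate of 0.125 mm/day. Estimating the SD from all three groups lowers the detectable differences by less than 0.01.

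**The case against.** The strongest objection concerns the SD. Its unit is not printed, and read as mm/day it is 2.5 times the G1 mean (.1 / .04). If 0.1 were per week (0.1 / 7 = 0.0143 mm/day), power at 0.125 mm/day would be near 1, and the detectable G2 vs G3 difference at 7 per group would be about 0.023 mm/day. At 0.125 mm/day and 7 per group, an SD of about 0.054 is enough for 0.8 on the overall test, and about 0.043 for the G1 contrast at 0.05/3. This stands as a condition on steps 4 and 5, although mm/day is the natural reading beside rates printed per day.

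Second, G1 could be compared with G2 and G3 combined. At 0.125 mm/day, two-sided at 0.05, that contrast has power 0.41, 0.56 and 0.72 at 7, 10 and 14 per group. It passes 0.8 only one-sided with all 14 per group retained (0.82), not at the 7 for which the plan makes its claim.

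Third, the planned analysis uses five time points, which may be more precise than one rate per patient. No within-patient correlation is given, so the gain cannot be computed.

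Fourth, the document is dated after its own timeline for data collection, so revised planning power may not alter the design. What the results can support still has to be stated correctly.

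None of this touches step 2. No choice of SD, test or repeated-measures model gives power for a difference planned at zero.

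**Conclusion.** The concern holds, and the power sentence is wrong as written. It cannot extend to G2 vs G3, the contrast behind the Hypothesis, because no vibration effect was specified; this conclusion needs no assumption about SD, sidedness or model.

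For the overall test and the G1 contrasts the sentence is right at .28 mm/day and fails at the bracketed 0.125 mm/day, where two-sided power stays below 0.8 at 7, 10 and 14 per group. That second conclusion rests on an SD of 0.1 mm/day and one rate per patient. The documents do not show which of the two rates was intended.

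**What to change.** In Methods section 3:

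1. Reconcile .28 mm/day with .5 mm in 4 days, print the unit of the SD, and recompute power. Keep a power statement only for the overall test and those G1 contrasts that still reach it, and name them.
2. State that no power is claimed for vibration (G2 vs G3).
3. Print the G2 vs G3 difference detectable with 80% power, with its assumptions. On the present SD this is about 0.16, 0.13 and 0.11 mm/day at 7, 10 and 14 evaluable per group (alpha 0.05), or 0.20, 0.16 and 0.13 (alpha 0.05/3). Recompute if the SD, its unit or the outcome changes.
4. Report G2 minus G3 with a 95% confidence interval, and do not read p ≥ .05 as absence of a vibration effect.

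The planned ANOVA and Bonferroni correction stay as they are. The cost is one recalculation, a reworded section and one reported interval, with no extra patients. The general power claim is lost, and if the rates reconcile to 0.125 mm/day with the SD unchanged, possibly no power statement survives.

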 - a. In this study, we propose a single-blinded (Invisalign faculty) randomized prospective paralleled clinical trial to investigate effects of AcceleDent vibration therapy on the efficiency of tooth movement, on the activation of gingival crevicular fluid biomarkers and on patient discomfort in conjunction with accelerated Invisalign therapy. Enrolled subjects will be randomly allocated into one of 3 groups: Standard Invisalign therapy (G1-control), Accelerated Invisalign therapy + vibration (G2) and Accelerated Invisalign therapy without vibration (G3). Patients allocated to the standard Invisalign group will change aligners every 2

weeks while the both intervention groups will change aligners every 4 days. Patients allocated to the vibration group will receive an AcceleDent Aura device and bite down on the mouthpiece for 20 minutes/day. The AcceleDent Aura device vibrates at a .25N (25 grams) force level with a 30 Hz frequency. Data collection will include intra oral scans of both the maxillary and mandibular dentition at 5 different time points: TO (baseline), T1 (4 days), T2 (14 days), T3 (6 weeks) and T4 (12 weeks). In addition, PerioPaper strips will be used to sample gingival crevicular fluid at each of the time points listed above. Research subjects will also be asked to complete a daily diary regarding their pain level during treatment. Treatment plans for enrolled patients will be created using Invisalign's proprietary software: Clincheck Pro®. To reduce treatment plan variability and reduce potential sources of error, [name], who is an "Elite Top 1% Invisalign provider" and also a member of the exclusive North American Invisalign Clinical Advisory Board, will approve each treatment plan. [name] will also be blinded to any patients participation within the study in order to eliminate potential bias.

2. Recruitment:

- a. Participants will be conveniently recruited from the sample population of individuals seeking Invisalign orthodontic therapy within the UNC Graduate Orthodontic Clinic. Benefits for participants will include complementary vibration therapy using the AcceleDent Aura device, which is an estimated value of \$800. Financial reimbursement will also be offered to offset any parking fees associated with the study.
- 3. Power Analysis:

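### A single published block size of 6, with no stated concealment or timing of release, could make up to 20% of allocations certain in advance if earlier ones are known

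*Combined protocol and SAP*

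**What the plan says.** Methods, section 4 (Randomization) has patients "randomly allocated into the 3 groups based on a block randomization with size 6" and adds: "The list will be independently generated by our study biostatistician". No other block size and no stratification is mentioned. Section 8 (Arms) plans equal groups: "Control Group (G1): 14 patients, standard Invisalign therapy with 2 week aligner schedule", "Intervention Group (G2): 14 patients, accelerated Invisalign + vibration" and "Intervention Group (G3): 14 patients, accelerated Invisalign + no vibration".

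Section 1 (Study Design) says "Enrolled subjects will be randomly allocated into one of 3 groups". The only blinded party it names is the Invisalign faculty member who approves treatment plans. It describes no sham device. Section 2 (Recruitment) draws patients by convenience from one graduate clinic, whereas the abstract describes consecutive recruitment.

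In section 7 (Clinical Trial Protocol), recruitment, consent and "Completion of the Inclusion/Exclusion Case Report Form" all fall at Visit 3, day 60. The device is first handed out at Visit 4, day 120. The first listed difference in aligner supply is at Visit 5, day 125. Section 6, criterion e, requires "Willingness and ability to comply with study procedures, attend study visits, and complete the study".

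The documents do not say how the next assignment is hidden, when randomization takes place, when staff learn the result, who enrols patients, or whether the block size is withheld from recruiters.

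**The concern.** With one known block size, anyone who can see the earlier allocations can count what is left in the block. Independent generation of the list does not prevent this, because it governs how the sequence is made and not who can anticipate it. Arms are recognisable from the device and the aligner schedule, and one clinic sees the whole sequence.

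There is also room to act on a prediction. Recruitment is by convenience, and criterion e calls for a judgement about future compliance. The Adverse Events section removes non-compliant patients from the study, so expected compliance bears on who remains in each arm. If the next arm can be guessed, expected compliance or severity of crowding could influence who is enrolled next. With 14 patients per arm, and an ideal of 7 per arm in the Power Analysis, a few steered enrolments could change the make-up of an arm.

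**Working it through.** The plan gives no predictability figure to reproduce, so this is a direct calculation.

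**Inputs.** Block size 6 (section 4); three arms of 14, total 42 (section 8). Hence 42/6 = 7 complete blocks. Equal allocation implies 6/3 = 2 places per arm per block, with 6!/(2!2!2!) = 90 equally likely orders.

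**Case A: the block size and every earlier allocation are known.**

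An allocation is certain when only one arm has places left:
- Positions 1 to 4: never.
- Position 5: when the last two places belong to the same arm, 3 × (2/6) × (1/5) = 1/5.
- Position 6: always.

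The expected number per block is 1 + 0.2 = 1.2, and 1.2/6 = 20.0%. Over 42 patients this is 8.4 on average, with a minimum of 7 (one per block) and a maximum of 14 (two per block).

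Probability that the best guess is right, positions 1 to 6: 1/3, 2/5, 1/2, 8/15, 3/5, 1. The mean is 3.367/6 = 56.1%, against 33.3% by chance.

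Probability that at least one arm can be ruled out: 0, 0, 1/5, 3/5, 1, 1. The mean is 2.8/6 = 46.7%.

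**Case B: the most recent allocations are not yet known at enrolment.** The same enumeration, hiding the latest allocations, gives:

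| Latest allocations unseen | Certain | An arm ruled out | Best guess right |
|---|---|---|---|
| 0 | 20% | 47% | 56% |
| 1 | 3.3% | 30% | 45% |
| 2 | 0% | 13% | 41% |
| 4 | 0% | 0% | 34% |

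**Which row applies?** The gap from Visit 3 to Visit 4 is 120 − 60 = 60 days. The recruitment period is not stated. As an assumption, spread 42 patients evenly over the roughly 19 months (about 580 days) from selection of the study population (August 2016) to the thesis defence (March 2018) in the Project Timeline. Then about 42 × 60/580 = 4.3 patients are consented in each 60-day gap. Faster recruitment means more unseen allocations. Fewer than one per gap would need 42 × 60 = 2,520 days, about 7 years. If arms become known only through Visit 4, the bottom row is therefore the closest. If assignments are announced at Visit 3, the top row is possible.

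**Effect of varied block sizes.** These figures are from simulation with N = 42. The recruiter knows the set of sizes and sees every earlier allocation. Where a range is shown, the lower figure is for lists cut off at 42 and the higher for sizes made to total 42.

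| Sizes | Certain | Best guess right |
|---|---|---|
| 6 only | 20% | 56% |
| 6 and 9 | 5.0-5.3% | about 54% |
| 3, 6 and 9 | 3.4-3.9% | about 55% |

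Varied sizes remove most of the certainty but little of the guessing advantage.

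**The case against.** The strongest objection is timing. The enrolment decision is made at Visit 3, while the visible signs of the arm begin at Visit 4, so a recruiter relying on those signs would learn little in time. This stands, and it is why 20% cannot be given without its condition. A reader might infer that recruiters will in fact know 20% of allocations. The documents do not support that, because they do not show that earlier allocations are known at consent. They do not secure the favourable timing either, since neither the moment of randomization nor the moment of disclosure is stated. If allocation were instead made at Visit 4, the order in which patients start treatment could still be anticipated.

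Three further inferences go too far:
- That eligibility is judged by the people who recruit. Section 7 assigns no role to either task.
- That the arm comparison is biased by some amount. The figures measure predictability, and nothing in the documents allows an estimate of bias.
- That a block of 6 is an error in itself. It is a legitimate choice and gives exactly 7 complete blocks and 14 per arm.

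It is also fair to say that release after consent and eligibility is compatible with the plan, which speaks of allocating enrolled subjects. It is not made explicit.

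**Conclusion.** The point holds in conditional form. The plan fixes and publishes one block size in a single-clinic trial with recognisable arms, and it describes neither concealment nor the time of disclosure. The share of allocations certain in advance lies between 0% and 20% on average. It is 20% (8.4 of 42) if the block size and all earlier allocations are known at enrolment, 3.3% if the latest one is unknown, and 0% if two or more are unknown. Best-guess accuracy runs from 56% down to 34%, against 33% by chance.

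This rests on two places per arm per block, which follows from three equal arms, and on list order following enrolment order. The missing description of concealment and timing is the larger gap, because it decides where in the range the trial falls. The fixed block size sets the upper end. Bias is possible and has not been shown.

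**What to change.** Have the study biostatistician prepare a list with randomly varied block sizes that total 42. Two examples are four blocks of 6 and two of 9 (24 + 18 = 42), or two of 3, three of 6 and two of 9 (6 + 18 + 18 = 42), with the order of sizes also random. In the protocol, say only that block sizes vary, and keep the sizes in a document that recruiters do not see.

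Add a short concealment paragraph stating who holds the list, who enrols, and at which visit the assignment is released and to whom. Release should come only after consent and the eligibility form are complete. This part is needed as well, because varied sizes alone leave best-guess accuracy at 54-55%.

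The cost is a new list and a few sentences. If recruitment stops mid-block, a block of 9 allows arms to differ by up to 3 patients, against 2 with blocks of 6.

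The document is dated August 2018 and its timeline has passed. If enrolment is under way, apply the change to the remaining allocations. If it is complete, report how assignments were concealed and when they were revealed.
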